## **8.0 Data and Quality Management, Confidentiality, Protocol Amendment**

### **8.1 Data Management**

All information will be collected according to the protocol and defined case report forms. Investigator subject records (e.g. medical records, imaging reports, or surgical notes) will be considered source documents for the study. This information will be entered by the site through a web-based portal provided by Wright Medical. Data will be received by Wright Medical through the EDC system. The Investigator must allow Wright Medical or its representative's access to the subject files. This access includes inspection of records.

In order to facilitate potential site monitoring visits, the investigator is required to keep records, including the identity of all participating subjects, all original signed Informed Consent Documents, and source documents. These records must be retained by the investigating site according to local regulations as specified in the Clinical Trial Agreement.

If the Investigator relocates, retires, or for any reason withdraws from the study, Wright Medical should be notified ahead of time. The study records must then be transferred to an acceptable designee (another investigator, institution, or Wright Medical). The investigator must obtain Wright Medical's written permission before disposing of any records.

### **8.2 Confidentiality**

The study team will ensure that the participants' anonymity is maintained. The participants will be identified only by study number on the electronic CRF. All documents will be stored securely and only accessible by study staff and authorized

|   |  |  |
|---|--|--|
|  | Clinical Investigation Plan
Foot and Ankle Products | CIP- INT19-MDR-001
Version: 2 |
|---|--|--|

personnel. To ensure confidentiality, none of the data stored or transferred electronically will contain personal identifiers.

### 8.3 Amending the Protocol

Amendments cannot be made to the study protocol without the written consent of Wright Medical. Additionally, amendments to the study protocol must be approved by the IRB/EC/REC prior to their implementation.

## 9.0 Deviations from the CIP

Investigators should not deviate from the study protocol except to deliver emergency care or to eliminate an immediate hazard to the subject. Deviations should be reported by completing the Protocol Deviation Case Report Form. Investigators must report all deviations from the study protocol to Wright Medical or its designated representatives. Additionally, any deviations found during monitoring visits must also be reported to Wright Medical or its designated representatives. All deviations with the potential to affect subject safety, rights, or well-being will also be reported to the IRB/EC/REC as soon as possible; based on the IRB/EC/REC requirements within the jurisdiction with each site.

## 10.0 Statement of Compliance

### 10.1 Institutional Review Board/Ethical Review Committee

It is the responsibility of the principal investigator at each participating site to obtain prospective approval of the study protocol, protocol amendments, Subject information sheets, Informed Consent documents, and any other relevant documents, if applicable, from the IRB/EC/REC. All correspondence with the IRB/EC/REC should be retained in the site's Investigator Master File. Copies of IRB/EC/REC approvals must be forwarded to Wright Medical or its designated representative prior to enrolling subjects. The Investigator must immediately report to Wright Medical or its designated representative if the IRB/EC/REC withdraws its approval of the study for any reason.

### 10.2 Statement of Compliance

This study will be conducted in accordance with ISO 14155: 2011-Clinical investigations, 21 CFR Part 11, 50, 54, 56, and the ethical principles originating from the Declaration of Helsinki, GCPs, and in compliance with local regulatory requirements. This study will be registered with ClinicalTrials.gov.

## 11.0 Adverse Events

### 11.1 Definitions

#### 11.1.1 Adverse Event (AE):

An AE or adverse event is:

Adverse event means any untoward medical occurrence associated with the use of an intervention in humans, whether or not considered intervention-related

**11.1.2 Serious Adverse Event (SAE)**

An adverse event is serious when it:

- Led to death
- Led to serious deterioration in the health the subject, that either resulted in
  - A life threatening illness or injury, or
  - A permanent impairment of a body structure or a body function, or
  - In-patient or prolonged hospitalization, or
  - Medical or surgical intervention to prevent life-threatening illness or injury or permanent impairment to a body structure or a body function,
- Led to fetal distress, fetal death or congenital abnormality or birth defect.

**11.1.3 Unanticipated Adverse Device Effect (UADE)**

An adverse reaction that is both unexpected (not consistent with the applicable product information) and also meets the definition of a Serious Adverse Event/Reaction

**11.2 Adverse Event Relatedness**

The relationship of the adverse event to the study device or the implant procedure should be reported on the adverse event data collection form.

- Device Related: An adverse event that results from the presence or performance of the device.
- Procedure Related: An adverse event that occurs as a result of the implant procedure.

**11.3 Adverse Event Assessment**

The subjects will be assessed for adverse events at the operative visit and post-operatively. The site will be given an adverse event case report form to complete. The information collected on the assessment will include the following:

- Date of event or onset
- Procedure related
- Device related
- Narrative of adverse event
- Treatment required
- SAE
- Subject withdrawal
- Hospitalization
- Adverse event outcome

- Mode of sponsor notification
- Date of resolution

The data provided on the adverse event case report form will be queried to assess as whether they were unanticipated and for severity. These will be reported accordingly

#### **11.4 Adverse Event Reporting**

[Reference: MDR Article 80 Recording and reporting of adverse events that occur during clinical investigations.]

##### **11.4.1 Investigators Reporting**

###### **Recording and Reporting Adverse Events - Investigator Responsibilities**

- Record protocol required AE's together with an assessment as recorded in the Adverse Event Case Report Forms;
- Supply Wright Medical, upon their request, with any additional information related to the safety reporting of a particular AE;
- If subject answers in patient survey in EDC system at visits (year 1-10) that a possible AE occurred, the site will contact patient to determine if an AE occurred and if yes, complete the Adverse Event Case Report Form.
- If the subject comes back to the site after the last scheduled follow-up but prior to study completion, the site should complete an Adverse Event Case Report form if the subject has experienced an AE.

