### **7.3 Data Analysis**

Improvements in subject quality of life after surgery will be assessed by constructing 95% confidence interval for the mean change from baseline score in EQ-5D-5L and FAMM total and component scores.

|   |  |  |
|---|--|--|
|  | Clinical Investigation Plan
Foot and Ankle Products | CIP- INT19-MDR-001
Version: 2 |
|---|--|--|

Survivorship of a Wright product will be assessed based on adverse event resulting from the presence or performance of the device. The Kaplan Meier survivorship method and life table analysis will be employed. Time to adverse event due to the presence or performance of the implant will be the survivorship endpoint for each Wright device. Also, time to reoperation to exchange or remove any part of the Wright device due to failure of the implant will also determine the Wright product survivorship. Subjects who will not experience these events will be censored at the last follow-up visit. The Kaplan Meier survival curve and the 95% Confidence Interval will be constructed.

Safety endpoints will include all adverse events (AE), serious AE (SAE), unanticipated adverse device effects (UADEs).

All subjects enrolled in the study will be assessed for safety. Adverse events and other safety evaluations will be reported as frequency and rates as appropriate, cumulative over the different follow-up schedules.

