## 8. Appendices

### 8.1. Appendix 1. List of Wright medical devices included in the study.

Device	Follow-Up Time Period
611 Nail	1 year
BIOARCH	1 year, 2 year
BIOFOAM Ankle Spacers	1 year
BIOFOAM Wedge System	1 year
CHARLOTTE MUC Screws	1 year
CHARLOTTE Quick Staple	1 year
CHARLOTTE Snap-Off Screws	1 year
CLAW II	1 year
DARCO Headed Screws	1 year
DARCO Headless Screws	1 year
DARCO MFS	1 year
DARCO MRS	1 year
DARCO Plantar Lapidus Plate	1 year
DART-FIRE	1 year
FUSEFORCE	1 year
FUTURA CSI	1 year, 2 year
G-FORCE	1 year, 2 year
GRAVITY SYNCHFIX	1 year, 2 year
HV Screws	1 year
MaxLock Edgelock Plate	1 year
MiniMaxLock ISO Plate	1 year
MICA Screws	1 year
NEXFIX Snap-Off Screws	1 year
Omni Evolution Screws	1 year
ORTHOLOC 2 Ankle Fracture	1 year
ORTHOLOC 2 CROSSCHECK	1 year
ORTHOLOC 2 Small Bones	1 year
ORTHOLOC 3Di Ankle Fusion	1 year
ORTHOLOC 3Di Hallux	1 year
ORTHOLOC 3Di Midfoot/Flatfoot	1 year
ORTHOLOC Forefoot Fracture	1 year
ORTHOLOC Plantar Lapidus	1 year
ORTHOLOC Calc Fracture	1 year
PHALINX	1 year
PITON	1 year
PRO-TOE VO	1 year
SALVATION ExFix	1 year
SALVATION Bolts and Beams	1 year
SALVATION 3Di Plates	1 year
SWANSON Toes	1 year, 2 year, 3 year, 4 year, 5 year, 6 year, 7 year, 8 year, 9 year, 10 year
Telya	1 year
UNIMA EVO and NEUTRA Screws	1 year
VALOR Nail	1 year

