## 8.2. Appendix 2 – Listing of Tables and Listings, Table Templates

### A. LISTING OF TABLES

Table	1.1	Subject Accounting
Table	1.2	Subject Eligibility
Table	1.3	Demographics and Clinical Characteristics
Table	1.4	All Protocol Deviations
Table	1.5	Medical History
Table	2.1	Surgical and Operative Information
Table	2.2	Additional Surgical Procedures Performed
Table	3.1	EQ-5D by device and visit
Table	3.2.1	FAAM score by device and visit
Table	3.2.2	FAAM overall rating by Device and Visit
Table	4.1	Surgeon assessment by device
Table	4.2	Radiographic assessment by device
Table	5.1	Life table for time to first device related adverse event by device
Table	5.2	Life table for device failure by device
Table	5.3	Life table for time to death by device
Table	6.1	Adverse event by device

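### Adverse events after the last scheduled visit are recorded only for subjects who have one, while event-free subjects are censored at that visit, so Kaplan-Meier and life-table device survivorship is biased downward

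*Protocol*

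**What the plan says.** Protocol 11.4.1 sets out what a site does once a subject's visits are over: "If the subject comes back to the site after the last scheduled follow-up but prior to study completion, the site should complete an Adverse" form, the sentence ending "Event Case Report form if the subject has experienced an AE". A subject who returns well generates no form, and nothing asks sites to contact those who do not return.

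Protocol 7.3 defines survivorship per device. "The Kaplan Meier survivorship method and life table analysis will be employed". There are two kinds of event: "Time to adverse event due to the presence or performance of the implant will be the survivorship endpoint for each Wright device", and "time to reoperation to exchange or remove any part of the Wright device due to failure of the implant". For everyone else, "Subjects who will not experience these events will be censored at the last follow-up visit".

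The SAP carries this forward only as table titles. Its Appendix 2A lists "Life table for time to first device related adverse event by device" (Table 5.1) and a life table for device failure (Table 5.2). The SAP body gives no censoring rule and no risk window. Appendix 1 of the SAP gives 1 year as the only follow-up period for 38 of 43 devices (for example "SALVATION ExFix 1 year"). Four devices have 2 years and one has visits to 10 years. Protocol 6.2.4 allows the whole study to run for up to 15 years.

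**The concern.** Kaplan-Meier and life tables assume that how long a subject is followed says nothing about whether the event will occur. Under these two rules, a subject's time on study extends past the last visit only if an event is reported there. The late risk set is then largely made up of cases, and each late event is divided by far too small a denominator.

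No passage in either document ends time at risk at the last visit, sets later events aside, or carries event-free subjects forward to a common date. An analyst who follows the text as written produces the bias. Protocol 2.0 says the results go to regulators and notified bodies as evidence of device safety, so a curve that drops to 0% when nearly all implants are event-free would mislead its readers.

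**Working it through.** **The plan's own figure.** The documents give no survival estimate. The only related number is the per-device sample size, which sets the scale here. With alpha 0.05 two-sided, SD 0.313 and half-width 0.1 (Protocol 7.2), n = (1.96 × 0.313 / 0.1)² = 37.6, rounded up to 38. This reproduces the stated value, and the plan takes 40. SAP 3.1 sets 10 implanted patients as the minimum for summarising a device.

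**The mechanism by hand.** The Kaplan-Meier estimate is S(t) = Π(1 − d/r), with d events among r at risk.

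- 39 subjects censored at 12 months and one device-related event at 20 months: r = 1, d = 1, S = 1 − 1/1 = 0. The crude event-free proportion is 39/40 = 0.975.
- 9 censored and one late event: S = 0 again. The crude proportion is 9/10 = 0.90.
- With k others still at risk at the event, S = 1 − 1/(k + 1): 0.50, 0.67, 0.80 and 0.90 for k = 1, 2, 4 and 9.
- Actuarial life table with yearly intervals: if censorings at exactly one year fall in the first interval, S = 0. If they fall in the second, with half-interval adjustment, S = 1 − 1/(N − (N − 1)/2), which is 0.82 for N = 10 and 0.95 for N = 40. The SAP does not state the convention.

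**How often.** Assumptions, none from the documents: hazard h of 0.01 to 0.02 per year for the survivorship event, sites open w years past each subject's last visit, 80% of affected subjects returning. The chance that a subject has a recorded late event is p = 0.8 × (1 − e^(−hw)), and the chance of at least one per device is 1 − (1 − p)^n.

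| w | p | n=10 | n=40 |
|---|---|---|---|
| 2 years | 0.0158 to 0.0314 | 15% to 27% | 47% to 72% |
| 6 months | 0.0040 to 0.0080 | 4% to 8% | 15% to 27% |

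**How large.** Simulation with the same assumptions and last visits uniform over 3 to 12 months (20,000 runs per setting). Events before the last visit are counted, late events are counted if the subject returns, and everyone else is censored at the last visit.

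| w | n | Mean final Kaplan-Meier, h = 0.01 to 0.02 |
|---|---|---|
| 2 years | 10 | 0.86 to 0.75 |
| 2 years | 40 | 0.58 to 0.35 |
| 6 months | 10 | 0.97 to 0.94 |

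The n=40 row should be read as good to about 0.02.

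**Comparator.** With w = 2 years the latest possible event is at 3 years, where true survival is e^(−3h) = 0.97 to 0.94. With w = 6 months the latest is at 18 months, where it is e^(−1.5h) = 0.985 to 0.97. The 6-month estimates are therefore still low, but only by about 0.02 to 0.03. Their match with the 3-year figures is a coincidence.

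**The case against.** A reader might infer that any late adverse event sends a device's curve to zero, or that most devices will end there. The documents do not support that.

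- Only a device-related adverse event or a reoperation for implant failure counts as a survivorship event, and zero needs that event to follow every other subject's last visit for the device.
- The yearly visits carry a window of plus or minus one year. If the 1-year entry in SAP Appendix 1 is that visit, month 20 may lie inside scheduled follow-up. If last visits were spread evenly over 6 to 24 months (an assumption), about 39 × 4/18 ≈ 9 others would remain at risk at month 20 and S would be about 0.90.
- The planned scale was not reached. SAP 3.1 says enrollment was stopped on 1 November 2021, with 122 patients enrolled and 40 per device not met. The 15-year duration is an outer bound, and how long sites stay open after a subject's last visit is not stated. The n=10 rows and the shorter window are therefore the more relevant ones.
- Other safety outputs are unaffected. The adverse event percentages in the SAP's Table 5.1 template are crude, and SAP 3.1 also plans the proportion surviving at each visit. Survivorship is not the primary endpoint and the SAP tests no hypothesis.
- Returning to the site is not strictly the only late route, because Protocol 11.4.1 also requires serious events to be reported when the investigator learns of them.

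All of this limits the size, but the mismatch remains. The serious-event route also depends on having an event. Protocol 7.3 does not say that its last follow-up visit means the last scheduled one, but counting unscheduled returns would help little, since no form is requested from a subject who returns well.

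**Conclusion.** The concern holds as a fault in the rule, not merely a missing detail. Followed as written, Protocol 11.4.1 and 7.3 make follow-up length depend on the outcome, and the per-device Kaplan-Meier and life-table survivorship is biased downward.

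The direction follows from the text. The amount does not: it rests on the assumed hazard, return rate, visit timing and time that sites stay open. On those assumptions it ranges from a shortfall of a few hundredths (n=10, 6 further months) to the loss of roughly 0.4 to 0.6 of the survival probability (n=40, 2 further years: 0.97 − 0.58 and 0.94 − 0.35). A final value of 0% is possible for a single device, but the documents do not show that it is likely for devices of the size now expected.

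**What to change.** In Protocol 7.3, and in a paragraph added to the SAP for the two life tables that Appendix 2A lists as Tables 5.1 and 5.2 (first device-related adverse event, device failure), define one risk window for all subjects:

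- Time at risk runs to the subject's last completed protocol follow-up assessment, with or without an event.
- An event counts if its onset is on or before that assessment, or if it falls in a follow-up interval whose status is ascertained for all subjects regardless of outcome. The second limb is needed because Protocol 6.2.2 discontinues a subject whose only study device is removed, and that subject may complete no further assessment.
- Later events go into a separate count or listing marked as after scheduled follow-up.
- Numbers at risk are shown, and the life-table interval convention is stated.

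Ending risk at the last scheduled rather than last completed assessment would not be enough. A subject who misses the visit would still be censored early if well and counted if an event brought them back. The SAP text should name the tables by title, because SAP 6.6 and its template use the number 5.1 for the crude adverse event table.

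The cost is a few sentences and a flag on adverse event records. Forms under 11.4.1 continue unchanged. The downside is that late spontaneous events leave the survival curve, although they are still reported. Ascertaining every subject's status to a common date would keep those events in the curve, but needs extra contacts.

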###### **Recording and Reporting Serious Adverse Events (SAE's) – (Immediately Reportable) Investigator Responsibilities**

- The investigator must report the following events to the Sponsor within 24 hours after learning of the event, regardless of relationship to study, using the appropriate SAE reporting form and guidelines;
- The investigator must report new significant follow-up information for these events to the Sponsor within 24 hours after becoming aware of the information. New significant information includes the following:
  - New signs or symptoms or a change in the diagnosis.
  - Significant new diagnostic test results.
  - Change in causality based on new information.
  - Change in the event/s outcome, including recovery.
  - Additional narrative information on clinical course of the event.

##### **11.4.2 Sponsor Reporting**

**Recording and Reporting Adverse Events - Wright Medical Responsibilities**  
Wright Medical is responsible for the classification of AEs and ongoing safety evaluation of the study and will:

- Review the Investigator's assessment of all AEs; determine and document, in writing, the seriousness of the adverse event and relationship of the adverse event to the implanted components.

In case of a disagreement between Wright Medical and the Investigator, Wright Medical shall:

- Communicate both opinions to concerned parties; and
- As required, ensure that the IRB/EC/REC and regulatory authorities are informed of significant new information involving the product during the study
- Or seek independent review as needed.

**Recording and Reporting Serious Adverse Events (SAE's) – Wright Medical Sponsor Responsibilities**

- SAEs must be summarized on the annual report to the IRB/EC/REC

**Recording and Reporting Unanticipated Adverse Device Effect (UADE)– Wright Medical Sponsor Responsibilities**

- UADEs must be reported to the IRB/EC/REC in accordance with GCP guidelines i.e. 7 or 15 day

## **12.0 Planned Clinical Investigation Closure, Early Termination of Clinical Investigation or Clinical Investigation Suspension**

### **12.1 Planned Clinical Investigation Closure**

The study will be considered complete once the last subject at the last active site has completed their study visits required by the study protocol. Additionally, the following activities must be completed at each site before the study is considered complete:

- All essential documents are complete and up to date;
- The Investigator has completed and submitted all required case report forms; and
- Arrangements are made for archiving and record retention.

All IRB's/EC/REC's have been notified of the conclusion of the study

### **12.2 Early Termination or Suspension**

Wright Medical reserves the right to discontinue the study at any time and will notify each investigator immediately at the time of such a decision. Formal documentation will be provided to the investigators to notify their IRB/EC/REC, research institutions. After such a decision, the Investigator must contact all participating subjects to notify them of this decision and its impact on their follow-up.

|   |  |  |
|---|--|--|
|  | Clinical Investigation Plan
Foot and Ankle Products | CIP- INT19-MDR-001
Version: 2 |
|---|--|--|

**12.3 Criteria and arrangements for suspension or premature termination of the whole CI or of the CI in one or more site(s).**

Wright Medical reserves the right to terminate a non-performing site. Reasons for considering early termination or suspension of an individual site may include, but are not limited to:

- Site non-compliance with study protocol or failure to comply with government or local regulations;
- Failure to submit data in a timely manner;
- Failure to comply with or act upon findings; and
- Failure to maintain pace to complete enrollment.

### **13.0 Publication Policy**

There isn't a plan to submit the data for publication

**DEVICE NAME:**

611 Nail  
BIOARCH  
BIOFOAM Ankle Spacer  
BIOFOAM Wedge System  
CHARLOTTE MUC Screws  
CHARLOTTE Quick Staple  
CHARLOTTE Snap-Off Screws  
CLAW II  
DARCO Headed Rearfoot Screws  
DARCO Headed Screws  
DARCO Headless Screws  
DARCO MFS  
DARCO MRS  
DARCO Plantar Lapidus Plate  
DART-FIRE  
FUSEFORCE  
FUTURA CSI  
G-FORCE  
GRAVITY SYNCHEX  
HV Screws  
MaxLock Edgelock Plate  
MiniMaxLock ISO Plate  
MICA Screws  
NEXFIX Snap-Off Screws  
Omni Evolution Screws  
ORTHOLOC 2 Ankle Fracture  
ORTHOLOC 2 CROSSCHECK  
ORTHOLOC 2 Small Bones  
ORTHOLOC 3Di Ankle Fusion  
ORTHOLOC 3Di Hallux  
ORTHOLOC 3Di Midfoot/Flatfoot  
ORTHOLOC Forefoot Fracture  
ORTHOLOC Plantar Lapidus  
ORTHOLOC Calc Fracture  
PHALINX  
PITON  
PRO-TOE VO  
SALVATION ExFix  
SALVATION Bolts and Beams  
SALVATION 3Di Plates  
SWANSON Toes  
Telya  
UNIMA EVO and NEUTRA Screws  
VALOR Nail

**STATISTICAL ANALYSIS PLAN  
(SAP) VERSION:**

1

**CLINICAL INVESTIGATION PLAN  
(CIP) VERSION:**

2

